## 9.3.5 Safety Variables

Safety of FEIBA NF assessed by using the following endpoints (see also Section 11):

- Incidence, severity and relatedness of SAEs
- Incidence, severity and relatedness of NSAEs
- Incidence, severity and relatedness of thromboembolic events and thrombotic microangiopathy
- Incidence in safety profile of FEIBA used on-demand and prophylactically based on assessment of all SAEs in the respective sub-group

## 9.3.5.1 Medical History, Medications and Non-Drug Therapies

At screening, the subject's medical history, including haemophilia and treatment history, will be described for the following body systems including severity (mild, moderate, or severe as defined in Section 11.2.4) or surgery and start and end dates, if known: eyes, ears, nose, and throat; respiratory; cardiovascular; gastrointestinal; musculoskeletal; neurological; endocrine; hematopoietic/lymphatic; dermatological; and genitourinary.

All medications taken and non-drug therapies received from enrollment until completion/termination will be recorded on the concomitant medications and non-drug therapies CRFs.

## 9.3.5.2 Physical Examination

Physical examination will be performed according to local routine at annual visits to the site. At screening, if an abnormal condition is detected, the condition will be described on the medical history CRF. At subsequent study visits, if a new abnormal or worsened abnormal pre-existing condition is detected, the condition will be described on the AE CRF. If the abnormal value was not deemed an AE because it was due to an error, due to a pre-existing disease (described in Section 11.2.6) not clinically significant, a symptom of a new/worsened condition already recorded as an AE, or due to another issue that will be specified, the investigator will record the justification on the source record.

#### 9.3.5.3 Clinical Laboratory Parameters

The investigator's assessment of each laboratory value will be recorded on the CRF. For each abnormal laboratory value, the investigator will determine whether the value is clinically significant or not. For clinically significant values, the investigator will indicate if the value constitutes a new AE (see definition in Section 11.1, and record the sign, symptom, or medical diagnosis on the AE CRF), is a symptom or related to a previously recorded AE, is due to a preexisting disease (described in Section 11.2.6), or was due to another issue that will be specified. If the abnormal value was not clinically significant, the investigator will indicate the reason, ie. because it is due to a preexisting disease, due to a lab error, or due to another issue that will be specified. However, additional tests and other evaluations required to establish the significance or etiology of an abnormal value, or to monitor the course of an AE should be obtained when clinically indicated. Any abnormal value that persists should be followed at the discretion of the investigator.

## 9.3.6 Subject Completion/Discontinuation

A subject is considered to have completed the study when he/she ceases active participation in the study because the subject has, or is presumed to have, completed all study procedures according with the protocol (with or without protocol deviations).

Reasons for completion/discontinuation will be reported on the Completion/Discontinuation CRF, including: completed, screen failure, adverse event (eg, death), discontinuation by subject [eg, lost to follow-up (defined as 3 documented unsuccessful attempts to contact the subject), dropout], physician decision (eg, progressive disease, non-compliance with medicinal product/protocol violation(s), recovery, disappearance of the inhibitor, success of the ITI treatment), study terminated by responsible party, or other (reason to be specified by the investigator, eg, technical problems). Regardless of the reason, all data available for the subject up to the time of completion/discontinuation should be recorded on the appropriate CRF.

The reason for discontinuation will be recorded on the CRF, and data collected up to the time of discontinuation will be used in the analysis and included in the clinical study report.

In the event of subject discontinuation due to an AE, clinical and/or laboratory investigations performed as part of the evaluation of the event will take place under the direction of the investigator and will be reported to the sponsor. Details of the outcome may be reported to the appropriate regulatory authorities by the responsible party.

#### 9.4 Data Sources

#### 9.4.1 Source Data

Source data are defined as all information in original records and certified copies of original records of clinical findings, observations, or other activities in a trial that are necessary for the reconstruction and evaluation of the trial. Source data are contained in source documents (original records or certified copies), which may be in paper and/or electronic format. Source data for this study comprise the following: hospital records, medical records, clinical and office charts, laboratory notes, memoranda, subject diaries or evaluation checklists, outcomes reported by subjects, pharmacy dispensing records, recorded data from automated instruments, copies or transcriptions certified after verification as being accurate copies, microfiches, photographic negatives, microfilm or magnetic media, imaging-rays, subject files, and records kept at the pharmacy, at the laboratories, and at medico-technical departments involved in the study.

## 9.4.2 Subject Diary

It is considered standard practice for subjects with hemophilia to maintain a diary which captures treatments and disease related data. A subject diary will be provided to each subject at the screening visit and at annual interval visit(s), as needed, to help with the standardization of data collection method. Nevertheless, the completion of the diary is a voluntary effort by the individual subject or subject's legally authorized representative. A subject diary should allow to capture the following information:

- Infusion log for FEIBA NF
- Bleeding episodes
- Effectiveness assessment for treatment of each bleed
- Effectiveness assessment for prophylaxis therapy
- Acute pain associated with hemophilia, as measured with individual bleeding
  episodes, using the NRS (or Wong Baker Face Scale). VAS can also be used if
  routine practice at the centre. Acute pain will be assessed by the subject for each
  bleeding event and reported on the diary
- Chronic pain will be assessed using NRS on annual basis or more frequently according to routine practice at the site.
- Number of days lost from school or work due to bleeding episodes or their treatment
- Adverse events
- Concomitant medications / Non-drug therapies
- Duration of infusion of FEIBA NF

Diary data will be captured remotely by the subject entering them into a particular part of the electronic CRF (e-CRF). During the study, the investigator has access to the database holding the subject diary data. Upon retrieval of subject diaries at site closure, the site will receive the pdf files with the subject entries, including the audit trail.

All AEs regardless of causality and the number of bleed occurrences recorded in the subject diary during study participation period will be transcribed onto the CRF. For other types of data, such as global effectiveness and pain assessments, in the subject diary, every attempt will be made to collect all data as stated in this protocol. There will be no imputation on any endpoint in this study. Therefore, missing data will be labeled as such.

#### 9.5 Study Size

As no hypothesis testing or interval estimation will be applied, the sample size for the study is not based on statistical considerations. The sample size of approximately 55 evaluable subjects was selected as a reasonable number for a non-interventional study to recruit in the two-year enrolment period planned for the study.

## 9.6 Data Management

#### 9.6.1 Data Collection Methods

The investigator will maintain complete and accurate paper format study documentation in a separate file. Study documentation may include medical records, records detailing the progress of the study for each subject, signed informed consent forms, drug disposition records, correspondence with the EC and the study monitor/sponsor, enrollment and screening information, CRFs, SAE reports (SAERs), laboratory reports (if applicable), subject diaries (if used), and data clarifications requested by the responsible party.

The investigator will comply with the procedures for data recording and reporting. Any corrections to paper study documentation must be performed as follows: 1) the first entry will be crossed out entirely, remaining legible; and 2) each correction must be dated and initialed by the person correcting the entry; the use of correction fluid and erasing are prohibited.

The investigator is responsible for the procurement of data and for the quality of data recorded on the CRFs. CRFs will be provided in electronic form.

If electronic format CRFs (e-CRFs) are provided by the responsible party, only authorized study site personnel will record or change data on the CRFs. All data should preferably be entered on the CRFs during the study visit. If this is not possible due to time restrictions, the data will be recorded on paper; this documentation will be considered source documentation. Changes to an e-CRF will require documentation of the reason for each change. An identical (electronic/paper) version of the complete set of e-CRFs for each subject will remain in the investigator file at the study site.

The handling of data by the responsible party, including data quality assurance, will comply with regulatory guidelines and the standard operating procedures of the responsible party. Data management and control processes specific to the study will be described in the data management plan (see Section 14.1).

#### 9.6.2 Software

All data processing, summarization and analyses will be performed with the SAS®, version 9.1.3 software or higher.

## 9.7 Data Analysis

## 9.7.1 Datasets and Analysis

The Safety Analysis Set (SAS) will consist of data for all subjects who were enrolled, met all inclusion and exclusion criteria, and received at least 1 infusion of FEIBA NF.

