# 9.1.2.4 Safety

- Incidence, severity and relatedness of serious adverse events (SAE)
- Incidence, severity and relatedness of non-serious adverse events (NSAE)
- Incidence, severity and relatedness of thromboembolic events and thrombotic microangiopathy (TMA events) (refer to Section 11.2.2)
- Incidence in safety profile of FEIBA used on-demand and prophylactically based on assessment of all SAEs in the respective sub-group

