# 9.2.3.2 Exclusion Criteria

Subjects who meet ANY of the following criteria are not eligible for this study:

- Subject has a known hypersensitivity to the product or any of its components
- Subject has other contraindications to FEIBA NF: FEIBA NF must not be used in the following situations if therapeutic alternatives to FEIBA NF are available:
  - > Disseminated intravascular coagulation (DIC)
  - Acute thrombosis or embolism (including myocardial infarction)
- Subject has any other severe concomitant clinically relevant bleeding disorder
- Subject has participated in another clinical study involving a medicinal product or device within 30 days prior to enrollment or is scheduled to participate in another clinical study involving a medicinal product or device during the course of this study.
- Subject is a family member or employee of the investigator

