#### 9.2.4 Informed Consent and Enrollment

Any patient who directly or indirectly through a legally authorized representative provides informed consent (ie, signs and dates the informed consent form - ICF - and assent form, if applicable) is considered enrolled in the study.

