## 9.7.3.8 Planned Interim Analysis of the Study

Only subjects that were enrolled and met all inclusion/exclusion criteria will be included in interim analyses.

The first study interim analysis is planned after all subjects are enrolled. All the following 3 interim study analyses will be available in May on annual basis in the period 2019-2021 Regular safety updates and study progress reports are to be scheduled.

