#### 21. Section 9 Research Methods

Description of Change: In "Data Analysis", in the "Datasets and Analysis" the specifications of the "EFAS", "HRQoLAS", "PEAS", "PDAS", "JHFAS" were cancelled

Purpose for Change: To simplify analysis, prevent bias and align with new templates

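### The Safety Analysis Set, the only analysis set defined, leaves out treated subjects who failed an eligibility criterion, which conflicts with the protocol's own text on adverse events and discontinued subjects

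*Protocol*

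**What the plan says.** Protocol section 9.7.1 defines a single set, the Safety Analysis Set, made up of "all subjects who were enrolled, met all inclusion and exclusion criteria, and received at least 1 infusion of FEIBA NF". The current text defines no other set. Section 9.7.3.8 repeats the condition: "Only subjects that were enrolled and met all inclusion/exclusion criteria will be included in interim analyses".

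Other sections bear on who this removes:

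- Section 9.2.4: anyone who gives informed consent "is considered enrolled in the study". Eligibility is a separate, later filter.
- Sections 9.1 and 9.2.3: FEIBA NF must already have been prescribed by the treating physician before study participation.
- Section 9.2.3.2: two of the five exclusion criteria are "Subject has a known hypersensitivity to the product or any of its components" and "Subject has other contraindications to FEIBA NF". The second names DIC and acute thrombosis or embolism, and applies where therapeutic alternatives exist.
- Section 9.1.2.4: a named safety endpoint is "Incidence, severity and relatedness of thromboembolic events and thrombotic microangiopathy".
- Section 11.1: adverse events are recorded from enrolment onward.
- Section 9.7.3.4: all adverse events are to be coded, summarized and cross-tabulated. No analysis set is named.
- Section 9.3.6: screen failure is one of the listed reasons for discontinuation, and "data collected up to the time of discontinuation will be used in the analysis".

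**The concern.** A safety summary should cover everyone exposed to the product. Here exposure does not depend on eligibility, because the drug is prescribed in routine practice before the study and consent alone makes a subject enrolled. A treated subject with an eligibility breach is exposed and has adverse events collected, but stands outside the only defined set.

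The filter is not clearly neutral for safety. Two of the criteria it enforces concern hypersensitivity and thrombotic risk, and thromboembolic events are an outcome that the study sets out to describe. Use of the product despite such a criterion is part of routine practice, which the study is meant to document. With about 55 subjects and a rare event, a single omitted case could decide whether a table shows one event or none.

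**Working it through.** The protocol gives no figure on this point to reproduce. The sample size of about 55 has no statistical basis (section 9.5). The check is therefore a comparison of sections, followed by an illustration.

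**Can a treated but ineligible subject exist?** Yes. Enrolment is by consent (9.2.4), the prescription precedes the study (9.1, 9.2.3), and adverse events are recorded from enrolment (11.1). None of these depends on passing the eligibility check.

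**What happens to that subject's data?**

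- Under 9.7.1, the subject is outside the Safety Analysis Set.
- Under 9.7.3.8, the subject is outside every interim analysis.
- Under 9.7.3.4, the subject's adverse events are summarized, if the reference to all adverse events is read literally.
- Under 9.3.6, the subject's data up to discontinuation are used in the analysis, even when the reason is screen failure.

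The first two statements cannot both be reconciled with the last two. Nothing in the text says which prevails, and no listing is planned for treated subjects outside the set.

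**Illustration of size.** Two inputs are assumptions that the protocol does not give: k treated but ineligible subjects in addition to 55 eligible ones, and one thromboembolic event, occurring in an ineligible subject. Intervals are exact (Clopper-Pearson) 95%.

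- Set as written: 0/55 = 0% (0 to 6.5%), whatever k is.
- All treated, k = 1: 1/56 = 1.8% (0.05 to 9.5%).
- All treated, k = 3: 1/58 = 1.7% (0.04 to 9.2%).
- All treated, k = 5: 1/60 = 1.7% (0.04 to 8.9%).

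The intervals overlap widely. What changes is whether the summary reports an event at all.

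**How likely is such an event?** Section 7.2 cites about 4 thrombotic events per 100,000 infusions, a spontaneous reporting rate. Assume 3 infusions weekly for 4 years, which is high for a cohort that includes on-demand treatment.

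- All 55 subjects: 55 × 4 × 52.18 × 3 = 34,439 infusions, and 34,439 × 4/100,000 = 1.38 expected events.
- 3 ineligible subjects: 3 × 4 × 52.18 × 3 = 1,878 infusions, and 1,878 × 4/100,000 = 0.075 expected events.

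At the cited rate, an event among 3 ineligible subjects would be unusual. Expecting one full event would need a rate about 1/0.075 = 13 times higher in them. The protocol neither states nor excludes such a rate.

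**The case against.** The strongest reply is that loss from the final tables is inferred. Section 9.7.3.4 refers to all adverse events and names no set, and section 9.3.6 says discontinued subjects' data are used. This stands in part: for the final tables the text shows a contradiction, not certain loss. For the interim analyses the exclusion is explicit.

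A second reply is that few subjects will be affected. Eligibility is checked at screening (Table 1), so long follow-up of an ineligible subject needs a breach missed there. Section 9.7.1.1 even treats enrolment as having met all criteria. It is fair that the number may be small, and the protocol gives none. The gloss in 9.7.1.1 does not agree with 9.2.4, however, and does not show that no such subject will occur.

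A third reply is that safety oversight is intact. Thromboembolic events and thrombotic microangiopathy are listed as examples of serious events (11.2.2), all serious events are reported within 24 hours, and regular safety updates are planned. This is correct, but expedited reporting does not supply the incidence that 9.1.2.4 asks for.

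A reader might go further and infer that the exclusion criteria are mainly safety criteria, so that the filter removes the subjects most likely to have an event. The documents do not support that. Only two of the five exclusion criteria bear on hypersensitivity or thrombosis, and the DIC and thrombosis item is conditional on alternatives being available. The others concern another bleeding disorder, other-study participation and a relation to the investigator. A subject whose first thromboembolic event comes after entry stays in the set.

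**Conclusion.** The point holds as a defect in a stated rule. The only analysis set, although named for safety, depends on eligibility. It can leave treated subjects out of set-based safety summaries and it contradicts sections 9.7.3.4 and 9.3.6. Relative to all treated subjects, incidence can be understated.

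No magnitude can be claimed beyond illustration. The difference between 1/58 = 1.7% and 0/55 = 0% rests on an assumed 3 ineligible subjects and an assumed event in one of them. A reader might infer from the 1.38 events expected in the whole cohort that the filter would remove most of the thrombotic signal. That does not follow, because those events are spread over all 55 subjects and only about 0.075 would fall among 3 ineligible ones at the cited rate. Nor do the events vanish from the record: they stay on the case report form, and serious ones are still reported. The study is descriptive, so no test or error rate is affected.

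**What to change.** - In 9.7.1, define the Safety Analysis Set as all enrolled subjects who received at least 1 infusion of FEIBA NF, regardless of eligibility.
- In 9.7.3.4, name this set as the basis for the adverse event tables.
- In 9.7.3.8, use it for the interim safety summaries.
- Keep the eligibility condition for the effectiveness (ABR) analyses only, where 9.7.1.1 and 9.7.1.2 already state it.
- List treated but ineligible subjects with the criterion failed and their adverse events.
- Align 9.3.6 with these sections, so that it is clear which data of a screen failure are used and where.

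The cost is wording in a few sections and one listing. No new data are needed, since adverse events are already collected from enrolment. The downside is that reported incidence may be slightly less favourable, and that safety and effectiveness denominators may differ by a few subjects.

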#### Exclusion criteria:

Subjects who meet **ANY** of the following criteria are not eligible for this study:

- Subject has a known hypersensitivity to the product or any of its components
- Subject has other contraindications to FEIBA NF: FEIBA NF must not be used in the following situations if therapeutic alternatives to FEIBA NF are available:
  - Disseminated intravascular coagulation (DIC)
  - Thromboembolic events (e.g., Myocardial infarction, Stroke, TIA, DVT, PE)
- Subject has any other severe concomitant clinically relevant bleeding disorder
- Subject has participated in another interventional clinical study involving a medicinal product or device within 30 days prior to enrollment or is scheduled to participate in another interventional clinical study involving a medicinal product or device during the course of this study
- Subject is a family member or employee of the investigator

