# 7.2 Medicinal Product Safety Profile

Overall, FEIBA NF was well tolerated as reported in Baxter internal studies and in published clinical evidence. No thrombotic complication was reported in two prospective, clinical trials on prophylaxis (ProFEIBA  and PROOF 31,i;ii). One thrombotic event deemed to be possibly related to FEIBA was reported in a prospective study on FEIBA use for surgery (SURF study).

The safety of FEIBA with regard to thrombotic adverse events, the major concern with all bypassing agents, was reviewed specifically in two publications.

Ehrlich et al. (2002) analysed adverse event (AE) data that had been reported spontaneously to the pharmacovigilance department at Baxter BioScience. The database also included AE reports identified through screening of current literature.

FEIBA NF 090701 Clinical Study Report, dated 14 Jan 2013, Table 10

FEIBA NF 090701 Clinical Study Report dated 14 Jan 2013, Section 12.2.3.2.1, page 76

Over a 10-year period, altogether 55 events of all types had been reported. Among them, 16 thrombotic AEs (29%) were documented, relating to Disseminated Intravascular Coagulation (DIC), acute myocardial infarction, pulmonary embolism and thromboses. There was a single fatality. The observed reporting rate of total thrombotic AEs for the compilation period was approximately 4 per 100,000 infusions. Known risk factors were evident in 81% of the patients with thrombotic events. The findings provide encouragement that the risk of thrombotic complications in patients receiving FEIBA is low.

Aledort (2004)  reviewed MedWatch (the United States FDA pharmacovigilance system) data on thrombotic complications for both FEIBA and rFVIIa between April 1999 (i.e. the time when rFVIIa was introduced for clinical use in the USA) and June 2002. It was concluded that thrombotic AEs following either FEIBA or rFVIIa are rare. Similar to the publication by Ehrlich et al. (2002), risk factors were identified in the vast majority of patients with thrombotic AEs. Documented experience also provides assurance that in the majority of patients with FVIII or FIX inhibitors, FEIBA achieves comparable hemostatic efficacy as would be expected in non-inhibitor patients treated with coagulation factor replacement therapy.

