# 9.2.3 Subject Selection Criteria

Subjects must have been prescribed FEIBA NF for the treatment or prevention of bleeding events by a treating physician prior to the decision to enroll in the study.

No additional diagnostic or monitoring procedures may be applied to subjects, except those that are part of normal/routine clinical practice.

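### The Safety Analysis Set is conditioned on eligibility, so adverse events in treated subjects found ineligible are collected but fall outside the safety result

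*Protocol*

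**What the plan says.** Section 9.7.1 of the protocol defines one analysis set, the Safety Analysis Set, made up of data for all "subjects who were enrolled, met all inclusion and exclusion criteria, and received at least 1 infusion of FEIBA NF". Section 9.7.3.8 repeats the restriction: "Only subjects that were enrolled and met all inclusion/exclusion criteria will be included in interim analyses". It makes no exception for safety.

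The sections that decide who can be exposed and observed are wider:

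- Section 9.2.4: a patient who gives informed consent "is considered enrolled in the study". Eligibility plays no part in this.
- Section 9.2.3: "Subjects must have been prescribed FEIBA NF for the treatment or prevention of bleeding events by a treating physician prior to the decision to enroll".
- Section 9.2.6: screening data go onto the CRF whatever the screening outcome.
- Section 11.1: AEs are recorded from enrolment to study completion.
- Section 9.3.6: screen failure is listed among the reasons for completion or discontinuation, and data up to discontinuation are to be analysed and reported.
- Section 9.7.3.4: every AE is to be coded, summarised and cross-tabulated. No analysis set is named.

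The safety endpoints in section 9.1.2.4 include "Incidence, severity and relatedness of thromboembolic events and thrombotic microangiopathy".

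**The concern.** A safety population is normally defined by exposure. Adding eligibility means that a subject who consented, received FEIBA NF during the study and is then found to breach a criterion leaves both the numerator and the denominator, although his AEs were collected.

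The filter is not neutral to the endpoint. Several exclusions are contraindications to the product: hypersensitivity, DIC, and thrombosis or embolism. Their presence is plausibly linked to the events that section 9.1.2.4 sets out to describe. If ineligible treated subjects have events more often than eligible ones, the reported incidence is too low. With about 55 evaluable subjects and a rare event, a single subject can decide whether the report shows an event or none.

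**Working it through.** There is no figure in the plan to reproduce. Section 9.5 states that the study size has no statistical basis, and no event rate per subject is given. The check has two parts.

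**1. Can a subject be enrolled, treated and ineligible?** Yes. Enrolment is consent (9.2.4). The prescription precedes the decision to enrol (9.2.3). The CRF is filled in whatever the screening outcome (9.2.6), and AE recording starts at enrolment (11.1). Under 9.7.1 such a subject's AEs fall outside the set. Under 9.3.6 and 9.7.3.4 they belong in the analysis. These statements cannot all be followed.

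Who counts as ineligible is also unsettled. The Abstract (section 4) names "Thromboembolic events (e.g., Myocardial infarction, Stroke, TIA, DVT, PE" among the exclusions, with no limit to acute events, while section 9.2.3.2 has "Acute thrombosis or embolism (including myocardial infarction". A subject with a past thromboembolic event could be in the safety set under one wording and out of it under the other.

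**2. What would one omitted event do?** The documents do not say how many ineligible treated subjects to expect, so the following is an assumption shown over a range. Take 55 eligible treated subjects (the planned evaluable number) with no event, and add k ineligible treated subjects with x events. Intervals are exact (Clopper-Pearson), two-sided 95%.

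- Set as written, any k: 0/55 = 0%. Upper limit = 1 − 0.025^(1/55) = 6.5%.
- All treated, k = 1, x = 1: 1/56 = 1.8%. Lower limit = 1 − 0.975^(1/56) = 0.05%. Upper limit = 97.5% point of Beta(2, 55) = 9.6%.
- k = 3, x = 1: 1/58 = 1.7% (0.04 to 9.2%).
- k = 5, x = 1: 1/60 = 1.7% (0.04 to 8.9%).
- k = 3, x = 2: 2/58 = 3.4% (0.4 to 11.9%).
- k = 5, x = 2: 2/60 = 3.3% (0.4 to 11.5%).

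If one eligible subject also has an event, the change for k = 1 is from 1/55 = 1.8% (0.05 to 9.7%) to 2/56 = 3.6% (0.4 to 12.3%).

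The direction depends on the event. Omitting an ineligible subject without an event only shrinks the denominator: with one event among the eligible, 1/55 = 1.82% against 1/56 = 1.79%. The bias is downward only if events are more frequent among the ineligible.

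**How likely is it?** Section 7.2 cites about 4 thrombotic AEs per 100,000 infusions. Assume 3 infusions a week, the minimum in the glossary's definition of FEIBA prophylaxis, or about 156.5 a year. One subject followed for 4 years receives 4 × 156.5 = 626 infusions, and 626 × 4/100,000 = 0.025 expected events. At five times that rate, also an assumption, the figure is 0.13. The cited rate is a spontaneous reporting rate, so these values indicate order of magnitude only. A screen failure would contribute much less follow-up.

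**The case against.** The strongest reply is that the loss is conditional and probably rare. It needs an ineligible subject who is treated and has an event, and the expected count per such subject is small. Safety is a secondary objective and no hypothesis is tested. SAEs still go to the responsible party within 24 hours, and section 9.7.3.8 schedules regular safety updates. All of this stands and limits the size of the point. It does not repair the definition, because expedited reporting does not supply the study's incidence tables.

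Three stronger readings are tempting, and the documents do not support them.

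- A reader might infer that the subjects at highest thrombotic risk are the ones removed. The DIC and thrombosis exclusion applies only where therapeutic alternatives exist, so subjects without an alternative are eligible and stay in. Eligibility is checked at screening only (Table 1), so a thromboembolic event during the study makes nobody ineligible. Other exclusions, such as being a family member or employee of the investigator, carry no stated thrombotic risk. Section 7.2 does say "Known risk factors were evident in 81% of the patients with thrombotic events", but it does not list those factors or equate them with the exclusion criteria.
- A reader might infer that such subjects are certain to be missing from every safety table. Sections 9.3.6 and 9.7.3.4 point the other way. What can be shown is a contradiction in which the only defined set omits them.
- A reader might infer that, as the only set defined, it also drops on-demand subjects who had no infusion and so raises the on-demand ABR. Sections 9.7.1.1, 9.7.1.2 and 9.7.3.1 give ABR its own conditions: eligibility and at least 90 days observed on regimen, with on-demand time starting at enrolment. They require no infusion for on-demand time.

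**Conclusion.** The definition is wrong as written and should be fixed. It conditions a safety population on eligibility, repeats the filter at every interim analysis, and contradicts sections 9.3.6 and 9.7.3.4. The possible consequence is a downward bias in AE incidence, including thromboembolic events and thrombotic microangiopathy. Its size cannot be derived from the protocol. In the simplest illustration, one event in one ineligible treated subject separates a reported 0/55 (upper limit 6.5%) from 1/56 (1.8%, 0.05 to 9.6%). That rests on the assumption that such a subject exists and has the event. No bias in ABR is shown, and the point does not call the study's effectiveness results into question.

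**What to change.** - In 9.7.1, define the Safety Analysis Set as all enrolled subjects with at least one FEIBA NF infusion during the study, regardless of eligibility. Use it for all AE tables and flag ineligible subjects in a listing.
- In 9.7.3.8, use this set for interim safety summaries.
- Name the set in 9.7.3.4, and align 9.3.6 with it for screen failures who were treated.
- Keep the eligibility restriction for effectiveness only, as 9.7.1.1 and 9.7.1.2 already state it.
- Reconcile the thrombosis exclusion between the Abstract and 9.2.3.2, so that it is clear who is flagged as ineligible.

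The cost is a few sentences of protocol text. No new data are needed, because AEs are already recorded from enrolment.
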